3. In two randomized trials, some infants were apparently “salvaged” by subsequent laparotomy that was performed due to clinical deterioration as determined by the surgeon.
4. In the UK trial, the majority of initial drain infants (74%) did undergo subsequent laparotomy for a variety of reasons and the survival rate of this group was higher (although not statistically significant) than the drain only group. Based on data from this trial there is no evidence that subsequent laparotomy is harmful.
5. In the Moss trial, only 9% of drain infants had early subsequent laparotomy, but 4 of 5 that did survived. This also provides some evidence that in this trial early subsequent laparotomy was not harmful.
6. Surgeons have access to older retrospective data regarding “salvage” laparotomy, the more recent prospective data summarized above, and most have established practice patterns regarding this question. There are no truly clear, convincing data supporting benefit or harm of this therapy. For sure, some infants do survive after early subsequent laparotomy.
7. Disallowing subsequent laparotomy does not appear to be a realistic option from an ethical standpoint.
8. Limiting subsequent laparotomy to instances in which there is clinical deterioration seems appropriate.

Based on the above literature review, we strongly discourage subsequent laparotomy after initial drainage during the first 12 hours post-drain. Trial infants will be very carefully and continually assessed for their response to the initial surgical therapy and if the patient’s condition is deteriorating further, subsequent laparotomy is allowed in the trial. For each operative intervention, the indications for the operation as well as details of the intervention will be recorded prospectively.

Follow-up Evaluation. Infants will be assessed at 18 to 22 months of age, corrected for prematurity, according to the NICHD Neonatal Research Network Follow-up Study Protocol (rev. 10.31.2007) and Manual (rev. 2.28.2008). The follow-up visit includes the following assessments or structured inquiries: medical history including neurosensory outcomes, physical and neurological examination, neurodevelopmental evaluation with the Bayley Scales of Infants Development III, social/behavioral evaluation with the Brief Infant Toddler Social Emotional Assessment (BITSEA), and demographics and socioeconomic status questionnaires. Examiners are certified according to the procedures described and approved by the NICHD Neonatal Research Network.

Neurodevelopmental impairment (NDI) is defined as meeting any of the following criteria: moderate to severe cerebral palsy (CP) with Gross Motor Function Classification System (GMFCS) Level ≥ 2 , a Bayley III Cognitive score < 85 , < 20 -200 bilateral vision, and/or permanent hearing loss that does not permit the child to understand the directions of the examiner and communicate despite amplification.

The components of NDI are defined as follows:

Cerebral Palsy: Definite abnormalities in classical neuromotor exam, including tone, deep tendon reflexes, coordination and movement, coupled with a delay in motor milestones with a disorder of motor function. Severity of CP is classified according to the GMFCS level.³⁰ Moderate CP is defined as GMFCS level 2 or 3; severe CP is defined as GMFCS level 4 or 5.

Psychometric testing: Cognitive outcome at 18-22 months will be assessed by certified psychologists or psychometricians using the BSID III. For this study, the cognitive subtest (mean \pm SD: 100 \pm 15) will be administered. Scores on the cognitive subtest of <70 (>2 SD below the mean) is consistent with severe cognitive impairment.

Sensory deficits are identified through specific question concerning vision and hearing. Children with no useful vision in either eye is consistent with a refraction definition of <20/200 (legally blind). Permanent hearing impairment that does not permit the child to understand the directions of the examiner and communicate despite amplification is consistent with severe auditory impairment and would be adequate to meet the definition of NDI.

An important issue (for this trial and for neurodevelopmental assessment of premature infants in general) is the potential difference in sensitivities of the Bayley II and III products in defining NDI. Some authors have reported recently that the Bayley III likely underestimates NDI, compared to the Bayley II.³¹ Because of these issues, for this trial a Bayley III score of <85 will be one of the conditions defining NDI (in addition to those above).

Blinding and Reliability. Blinded collection of predischarge data would not be reasonably feasible for our research nurses. Follow-up personnel who are not told the treatment group will assess all follow-up findings. Because patients in each treatment group are likely to require laparotomy after the initial surgical procedure, it will be difficult to predict treatment group assignment at 18-22 months by simply examining the child, as infants in both groups may have undergone multiple abdominal procedures. The final assessment of impairment will be reviewed by three subcommittee members without knowledge of treatment group who will adjudicate the outcome of any infants whose outcome is uncertain (as was done Hypothermia trial).

Statistical Analyses. The primary analysis will assess the effect of treatment on death or NDI at 18-22 months corrected age. This analysis will be performed using standard statistical analyses often used in multicenter trials: logistic regression equations in which the predictor variables include treatment group and the stratifying variables (in this trial, center, and risk stratification formula). The analyses will include an assessment of whether there is an interaction between treatment (laparotomy or drainage) and disease (NEC or IP). Bayesian analyses^{11, 15} of the primary outcome will also be performed because statistical power will be limited to identify treatment effects that are clinically important but smaller than hypothesized and because Bayesian analyses can be used to estimate the (posterior) probability that laparotomy reduces death or NDI at 18-22 months.

To avoid bias in selecting the final regression model for the risk adjusted analyses of the nonrandomized patients, the baseline predictors will be determined before the logistic regression analyses are performed. Selection will be based on biologic plausibility, the results of our prior observational study, and univariate analyses of trial results. Likewise the baseline variables used in the final models for propensity scoring will be determined before any of these analyses are performed. Diagnosis & prognosis will be assessed using methods developed in our prior observational study. Nominal p values will be calculated for secondary outcomes without adjustment for multiple comparisons. Exploratory subgroup differences will be performed.

We plan to collect the same data for eligible, non-randomized infants (with consent) as for randomized infants. This will allow comparison of the patient characteristics and outcomes in the randomized and non-randomized cohorts and perhaps assess the external validity of our study findings (generalizability). As a secondary analysis, the risk adjusted relative risk will be determined in the randomized & preference groups and the value of combining these cohorts will be evaluated. This approach, known as a comprehensive cohort design, has been recommended in a recent meta-analysis for rare diseases or for evaluation of emergency therapies.¹⁰ Whether this approach is useful or not will be a secondary aim and these analyses will not affect the primary analysis of the randomized cohort.

Currently, there is unavoidable uncertainty about differences between the Bayley II and III outcomes. Based on Network GDB data available at this time, it appears that a Bayley III score <85 best approximates that of a Bayley II <70 which has been previously used by the Network in the definition of neurodevelopmental impairment. As this trial progresses, an increasing body of data will accumulate regarding the differences in

the Bayley tests. We plan to critically examine these data (GDB data, pooled data from NEST study subjects, and publicized data from other studies) at yearly intervals during the trial enrollment period. The sample size determination will be reevaluated, and may be revised upwards as the uncertainty regarding the Bayley III lessens (2 years after study commencement). These decisions will be made by the Steering Committee based upon a recommendation by the NEST subcommittee, and without any knowledge of the difference between the two treatment groups in this trial with regard to the proportion of impaired children.

Sample Size. Allowing for a smaller difference between treatment groups in the trial than in our observational study, we hypothesize that 80% of the drain group and 65% of the laparotomy group will die or be impaired at 18-22 mo. (Number needed to treat = only 7 to gain one unimpaired survivor from laparotomy). By PASS software, a total sample size of 300 infants who have their outcome assessed is needed with $\alpha = 0.05$ and $\beta = 0.20$ using 2-sided Fisher exact test.

In the observational study 156 infants were enrolled in 14 centers in 18 months. By extrapolating these numbers to a 16-center trial design, 120 eligible patients / year would be expected. Based on the latest GDB data, using the 16 centers prior to reformatting the Network, an estimated number of eligible babies of 190 is obtained. Our best estimate of the number of eligible patients in the new 16-center Network is 160 / year. We anticipate a 50% enrollment rate, $\geq 95\%$ consent for data collection (as for generic data collection), equal use of initial laparotomy and drains; and a 50% mortality in each group. Assuming a consent rate of 50%, 320 patients would be enrolled in a 4-year period with 160 deaths and 160 survivors. With a 90% follow up rate, 144 survivors would have the primary outcome measured. This would yield 304 patients which will meet our sample size requirement during a 4-year enrollment period. If the consent rate is below 50%, the enrollment period would need to be extended.

We propose that the trial be stopped when any of the following are met: 1) DSMC might stop trial for large difference in neonatal mortality (secondary outcome), which is unlikely given equivalent survival in both observational study and two randomized trials; 2) 300 randomized patients are enrolled and have primary outcome assessed; or 3) a 5-year enrollment period has elapsed.

Interim Monitoring. Adverse events during the course of the trial treatment period will be prospectively monitored, as will clinical morbidities throughout hospitalization. The enrolled population is extremely high risk, and their hospitalization can produce a great number of expected adverse events and clinical diagnoses. Rates of these events, historically observed among similar extremely low gestation/birth weight infants, will be provided to the Data Safety Monitoring Committee (DSMC). Secondary outcomes of interest in this trial that can be compared across the two treatment groups include death; death or prolonged parenteral nutrition; specific surgical complications such as wound dehiscence, intestinal stricture or fistula, procedure-related liver hemorrhage; number of surgical procedures; sepsis episodes; duration of parenteral nutrition; parenteral nutrition associated cholestasis; length of hospital stay; rehospitalizations; and each component of the primary outcome (available only after the 18-22 month follow up visit). The set of common, serious neonatal morbidities as defined in the NICHD Neonatal Research Network (NRN) Generic Data Base (GDB) will also be collected and analyzed in all subjects. These include data on in-hospital growth, the incidence and severity of intraventricular hemorrhage and periventricular white matter damage, seizures, patent ductus arteriosus (PDA) and its treatment, nosocomial sepsis (and organisms), hearing impairment, in-hospital ROP, pneumothorax, and bronchopulmonary dysplasia.

Adverse events that are worse than mild or moderate, are unexpected or unanticipated, and possibly related to the study treatments will be reported within 48 hours of discovery to the Data Coordinating Center (DCC), to NICHD, and to the site Institutional Review Board (IRB). NICHD and the NRN DCC will determine if the event warrants expedited reporting to the Chair of the NRN DSMC.

The NRN DSMC will review and will need to approve the protocol before enrollment begins. The members of the DSMC are independently appointed by the NICHD and include representation from neonatologists, biostatisticians, clinical trialists, and ethicists. The DSMC reports to the head of NICHD.

The DSMC provides a summary of its conclusions after each meeting to each study site as prepared and distributed by the NRN DCC.

Note that the treatment in this trial will be conducted during the first few weeks of life for most study subjects, while the primary outcome of death or neurodevelopmental impairment will be assessed at 18-22 months of age. Thus, interim monitoring for this trial will be based primarily on monitoring adverse events (chiefly, death). For the first 120 randomized enrollees, the DCC will track rates of neonatal mortality and generate pre-specified tables after each 30 enrollees reach the Network Status (death, discharge, transfer or 120 days of age). Thereafter, if no trends of differences between groups were to develop, these comparisons will be done after every 60 enrollees reach Network status. The computed statistic at each of these safety looks will be compared to Pocock boundaries that are constructed beforehand so that an overall alpha level of 5% is maintained. If any trends of differences between groups were to develop, the DCC would notify the DSMC.

There will be annual DSMC meetings convened to monitor the progress of the trial and review the accruing safety data, starting one year after at least 11 sites have IRB clearance to start enrolling into the trial. Once follow up data start becoming available (which should occur from the 2nd year onwards) interim efficacy data will also be presented to the DSMC. To control for the inflation of Type I error associated with sequential testing, O'Brien-Fleming boundaries will be calculated. Since we cannot precisely predict beforehand what proportion of trial enrollees will have primary outcome data available before each of these meetings, we will use Lan DeMets spending functions to adjust the O'Brien-Fleming sequential monitoring bounds to account for unequally spaced interim analyses. In order to ensure the safety of participants, this monitoring regime ensures that adverse events are monitored more frequently than measures of efficacy, and the statistical bounds used to detect group differences in adverse event rates are more liberal than those used to determine efficacy. All data presented to the DSMC will be blinded to treatment group, though the report may be unblinded at the DSMC's request.

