
Analysis & Interpretation. The primary outcome (death or NDI at 18-22 months corrected age) will be analyzed in standard logistic regression equations in which the predictor variables include center, and level of risk at enrollment as determined by the method described above. Separate analyses will be used to assess whether there is an interaction between treatment (laparotomy or drainage) and disease (NEC or IP). Secondary analyses of randomized patients will be performed using Bayesian methods to assess the (posterior) probability that laparotomy reduces death or NDI relative to that with drainage.

Consent to randomization may be unobtainable before surgery for a sizable proportion of infants. Providing parents at least agree to collection of the same baseline and outcome data as for randomized infants, we will relate surgical treatment to risk adjusted outcome. A finding that the risk adjusted relative risk in the nonrandomized patients is similar to the relative risk observed in the randomized patients will support the validity of the trial results and generalizability of the results among randomized patients to nonrandomized patients. (This would be expected based on a prior meta analysis of studies using a comprehensive cohort design [JAMA 2005]). Whether use of propensity scoring also supports the results among randomized patients will also be assessed.

Sample Size and Resources. Based on our observational study, we hypothesize that 80% of drain infants and 65% of the laparotomy infants will die or be impaired (NNT = only 7 to gain one unimpaired survivor); 300 infants (150 / group) whose primary outcome is determined will be needed (alpha =0.05 & beta = 0.20, two sided Fisher exact test). Enrollment will likely require 4 years (assuming a consent rate of 50%) unless the consent rate is higher than projected. We propose to initiate this trial within Network sites initially given the importance and urgency of the clinical question. Enrollment will be prospectively monitored and if found to be low after 6 months (after 80% of participating centers have IRB approval and are actively participating in the trial), consideration will be given to add additional sites. Despite the difficulties anticipated with the proposed trial, the total expense and effort required will be small relative to other Network trials, and the trial may facilitate future trials involving urgent/emergent therapies, rare diseases, or surgical interventions.

TRIAL OBJECTIVES

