We are proposing to conduct this trial purely within the Network as long as adequate enrollment can be achieved. If enrollment is below the predicted rate that would allow completion of the trial in 4 years, we would propose to add additional sites as needed to allow adequate enrollment. Both randomized trials published in this area have been halted prior to achieving the desired sample size. It would be unwise to ignore this history. Thus, we propose to critically evaluate actual versus desired enrollment at 6 months and carefully consider the need / desirability of recruiting additional sites.

Comprehensive cohort design. This design differs from that of a conventional randomized trial by including not only patients whose treatment is randomly assigned but also any whose treatment is based on the preference of the physician or patient (or surrogate). When properly performed, every effort is made in these trials to promote clinical equipoise and obtain informed consent to be randomized. If such consent is refused, consent is sought only for data collection. Whenever possible, the determination of primary outcome is carefully standardized and assessed by masked evaluators. Baseline data are carefully collected and controlled during analysis to adjust for baseline differences between patients who receive different therapies.

This approach has the potential advantage of increasing the number of patients studied and the external validity (generalizability) of the results by involving patients and physicians who otherwise would not be involved.¹⁰ However, an increase in external validity would be important only if the internal validity of the results is not undermined. Based on surveys of purely observational studies, one would expect that inclusion of preference groups would bias the results. This problem might be avoided or minimized because of measures to promote equipoise prior to the study, stringent features of study design and analysis as noted above,

exclusion of centers with such strong biases that they are unwilling to randomize any patients, and the balancing of biases within and between centers that do participate. A systematic review published in JAMA this year¹⁰ assessed all trials using a comprehensive cohort design. The review concluded that “Differences in outcome between randomized and preference groups were generally small, particularly in large trials and after accounting for baseline measures of risk”.

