In the proposed study, we will use risk adjusted relative risk to assess whether the results for randomized patients are generalizable to nonrandomized patients. If the findings for randomized and nonrandomized patients favor the same surgical therapy (as we would expect from the findings noted above for comprehensive cohort studies), we would presume the results are generalizable to the nonrandomized patients. If the findings are different, we could not be certain whether the difference resulted from chance, true differences in effectiveness for randomized and nonrandomized patients, residual confounding that could not be adequately adjusted in the analysis, or other reasons. However, the last reason would be most likely if as in prior studies, nonrandomized patients treated with drains are at systematically higher risk than those treated with laparotomy (due to severity of illness, time of day, or other factors). Such risk factors may be quite difficult to adequately assess.

The analytic approach noted above is a different and more conservative analytic plan compared to a true comprehensive cohort study. However our trial provides an excellent opportunity for the Network to explore whether analysis conducted as if our trial used a comprehensive cohort design would provide similar results as for a conventional randomized trial in a setting where there is considerable effort to minimize bias.

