Analyses Using Propensity Scoring. Propensity scoring (which indicates the probability that individual patients will receive different therapies) has been advocated for use assessing treatments in observational studies when randomization is not feasible. There is ongoing controversy about the extent to which estimates of treatment effect obtained using propensity scoring may be biased by their use.²²⁻²⁵ We will use this trial as an opportunity to compare the relative risk for the primary adverse outcome with laparotomy among nonrandomized patients with that among randomized patients. As for conventional risk adjusted analyses noted above, results using propensity scoring for nonrandomized patients that favor the same surgical therapy found to be superior among randomized patients would support the generalizability of results obtained for randomized patients. If the findings are different, we could not be certain whether the difference resulted from chance, true differences in effectiveness for randomized and nonrandomized patients, or residual confounding that was not avoided by propensity scoring .

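### The protocol's Background treats agreement in direction between randomized and nonrandomized infants as generalizability; the abstract and SAP ask for similar relative risks, and neither document says that confounding could itself create agreement

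*Protocol*

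**What the plan says.** The two documents describe the comparison between cohorts in several places.

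- **Protocol, Comprehensive cohort design (under Background/Previous Studies).** The condition is "If the findings for randomized and nonrandomized patients favor the same surgical therapy" and the consequence is "we would presume the results are generalizable to the nonrandomized patients". The next sentence deals with disagreement: "If the findings are different, we could not be certain whether the difference resulted from chance", followed by true differences, residual confounding and other reasons. The section also raises, conditionally and with reference to prior studies, that "nonrandomized patients treated with drains are at systematically higher risk than those treated with laparotomy", and adds that such factors are hard to measure. Earlier it says of preference groups in general that "one would expect that inclusion of preference groups would bias the results".
- **Protocol, Analyses Using Propensity Scoring (also Background).** The same directional test, more softly worded: "results using propensity scoring for nonrandomized patients that favor the same surgical therapy found to be superior among randomized patients would support the generalizability". Chance and residual confounding again appear only under disagreement.
- **Protocol abstract, Analysis & Interpretation.** A different criterion: "A finding that the risk adjusted relative risk in the nonrandomized patients is similar to the relative risk observed in the randomized patients" is what supports validity and generalizability.
- **Protocol, Statistical Analyses.** No rule is given. The section says that these analyses will not affect the primary analysis of the randomized cohort.
- **SAP, Overall Study Design and Plan.** Similar results after proper adjustment give some evidence of generalizability.
- **SAP, Propensity Analysis.** A covariate-balance decision comes first. The RR point estimates and CIs are then compared informally.
- **SAP, Combined Analysis.** Same direction, on either the risk-adjusted or the propensity-adjusted estimate, is the trigger for an exploratory random-effects pooled RR, provided that the nonrandomized analysis is judged useful.

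Neither document defines *similar*.

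**The concern.** The Background reasoning is asymmetric. Disagreement between the cohorts is open to doubt from chance and confounding, while agreement is accepted without either caveat. But the bias that the protocol itself describes has a direction. If sicker nonrandomized infants tend to receive drains, incomplete adjustment makes laparotomy look better, which is also the hypothesized direction. Agreement in favor of laparotomy is therefore what residual confounding would tend to produce, and neither document says so.

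The criterion also ignores size. RRs of 0.80 and 0.99 agree in direction, but few readers would call them similar. One report could follow the Background and claim generalizability while another followed the abstract or the SAP and declined to, from the same two estimates. At stake are the wording of the conclusion on Secondary Hypothesis 1 and the reading of the exploratory pooled RR.

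**Working it through.** **Inputs from the documents.** Event rates of 80% (drain) and 65% (laparotomy) give RR 0.65/0.80 = 0.8125. The randomized cohort has 150 assessed infants per arm. The stated design reproduces: two-sided Fisher exact power at 150 per arm is 80.3%, against 80% stated. The documents attach no figure to the direction rule.

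**Assumptions.** The preference cohort has n = 50 or 150 infants per arm. *Favor* means the sign of the point estimate. Residual bias is RR 0.90 or 0.95 toward laparotomy. The documents give none of these. For context on size, the planning rates in Sample Size (120 to 190 eligible infants a year, half not randomized, 95% consenting to data collection, equal use of the two operations) imply, over the 3.44 years from the protocol date to 14 February 2013:

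- 120 × 0.50 × 0.95 × 3.44 / 2 = 98 per arm
- 190 × 0.50 × 0.95 × 3.44 / 2 = 155 per arm

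This is before loss to follow-up, and enrollment started only after ethics clearance, so it is context and not a bound.

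**Step 1. Standard error (SE) of log RR** = √[(1−p₁)/(p₁n) + (1−p₀)/(p₀n)].

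| Scenario | n = 50 | n = 150 |
|---|---|---|
| No effect, both arms 72.5% | 0.123 | 0.071 |
| 65% vs 80% | 0.126 | 0.0725 |

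**Step 2. Chance that the preference cohort points the same way.**

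| Truth in the preference cohort | n = 50 | n = 150 |
|---|---|---|
| No effect, no bias | 50% | 50% |
| No effect, bias 0.95: Φ(0.0513/SE) | 66% | 76% |
| No effect, bias 0.90: Φ(0.1054/SE) | 80% | 93% |
| True RR 0.8125 in both cohorts, no bias | 95% | 99.6% |

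The bias rows give the chance that the cohort favors laparotomy.

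**Step 3. What agreement is worth.** Given a randomized result favoring laparotomy, the likelihood ratio for RR 0.8125 against an unbiased null is 0.951/0.5 = 1.90 (n = 50) or 0.998/0.5 = 2.00 (n = 150). Against a null with bias 0.90 it is 0.951/0.804 = 1.18 or 0.998/0.931 = 1.07. Putting the same bias on both sides gives 1.07 to 1.23. Agreement is weak evidence, and close to none if such bias is present.

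**Step 4. Stricter reading.** If *favor* required two-sided significance at 5%, a null cohort would favor laparotomy about 2.5% of the time and a cohort with true RR 0.8125 would do so 38% (n = 50) or 82% (n = 150) of the time.

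**Step 5. The ratio of RRs.** The cohorts are separate, so SE = √(SE₁² + SE₂²) = √(0.123² + 0.071²) = 0.142 for n = 50, and 0.101 for n = 150. The 95% CI factor exp(1.96 × SE) is 1.32 or 1.22. For observed RRs of 0.80 (randomized) and 0.99 (nonrandomized), the ratio is 0.99/0.80 = 1.24, with 95% CI 0.94–1.64 (n = 50) or 1.02–1.51 (n = 150).

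**Step 6. Link to the SAP's Q.** With two estimates, Q = (difference in log RR)²/(v₁ + v₂), which is the squared z statistic of the log ratio.

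**Step 7. The pooling trigger.** Two million simulated pairs per setting were put through the SAP's random-effects formulas. The true RR was the same in both cohorts, the risk-adjusted estimate was pooled, and the correlation between the two adjusted estimates was assumed to be 0.5 to 0.95. With no effect, the pooled 95% CI misses the truth in 5.6–6.9% of triggered analyses, against 3.7–3.8% ungated. At RR 0.8125 there is no excess (3.5–3.8%). The SAP's prior usefulness condition is not modelled.

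**The case against.** The strongest reply is that the direction rule is not operative. Both statements sit in the Background, before Methods begins. The protocol's Statistical Analyses section has no such rule. The SAP, which sets out the planned analyses in more detail, asks for similarity, claims only some evidence, checks covariate balance first and compares estimates with their CIs. An analyst following the SAP would not apply the Background test. This stands, and it is why the point is low in severity.

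A reader might infer that the protocol says one thing throughout and the SAP another. The documents do not support that: the protocol abstract already uses *similar*, so the protocol is inconsistent with itself and the SAP matches its abstract. A reader might also infer that bias is ignored. It is not. The protocol expects preference groups to be biased, and the SAP calls its adjustment an attempt and says that the cohort is not representative. Only the statement that bias can produce agreement is missing.

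The percentages depend on an assumed cohort size, an assumed bias and a sign-only reading. The propensity section speaks of the therapy found superior among randomized patients, which may imply more than a sign. That also stands.

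Finally, the ratio has no threshold, and when pooling goes ahead the SAP's Q already carries the same contrast. So the ratio mainly adds clear display, and is new chiefly when pooling is not triggered. It still shows the size and precision of the difference directly, which two intervals compared by eye do not.

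**Conclusion.** The concern holds in limited form, at low severity. The Background sections infer generalizability from direction alone and leave out the caveat that matters most, since the confounding they describe would favor laparotomy. This conflicts with the protocol abstract and with the SAP. The effect is confined to the interpretation of Secondary Hypothesis 1 and the exploratory pooled RR.

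A reader might go further and conclude that the generalizability analysis is invalid or that the trial's main result is exposed. The documents do not support either: the SAP does not use direction to judge generalizability, and the protocol shields the primary analysis. Nor do the calculations show that bias of 0.90 is present. They show only that, if residual bias of that order remained, a sign-only rule could barely detect it. That the logic is one-sided is clear from the text; the size of the effect is known only under the stated assumptions.

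**What to change.** 1. In the two Background sections, remove the inference from same direction alone, and reconcile the wording with the protocol abstract and the SAP.
2. In the SAP's propensity section, add to the informal comparison the ratio of RRs (nonrandomized/randomized) with its 95% CI. Give it for the risk-adjusted estimate and, where the balance check allows, for the propensity-adjusted estimate.
3. Interpret generalizability from the range of ratios that the CI allows, not as pass or fail, and state that a CI including 1 does not prove similarity.
4. State that agreement favoring laparotomy may also reflect residual confounding by severity.
5. If the pooled RR is reported, show Q and the ratio beside it, and say that pooling was conditional on same direction.

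The cost is wording plus one ratio and CI per estimate, from RRs and standard errors that the SAP already produces. The downside is imprecision. Under the assumed sizes the CI spans a factor of about 1.22 to 1.32 either way, and with true RRs of 0.8125 and 1.0 it would still include 1 in 47–69% of trials (n = 150 to 50). The generalizability claim may therefore have to be weaker.
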